Configurations for adjustable levels of restraint are: 1) no tie for a calm patient, 2) resistance tie (intermediate level of restraint) for a patient with flailing arms OR for resistance exercise as might be supervised by a physical therapist or nurse, and 3) rigid tie for temporary tighter restraint for an agitated or aggressive patient or as a temporary restraint during a procedure when the arm must be immobilized.

2. An evaluation in healthy subjects demonstrated that the first *Exersides*TM prototype was feasible to use and comfortable for subjects. The prototype was tested in 6 registered nurse (RN)

Figure 1. *Exersides*TM restraint prototypes in use.

A: Healthy volunteer able to move arm from the shoulder but the restrained hand is unable to self-extubate or remove the device. Adjustable levels of restraint possible using resistance or rigid (white) straps. **B:** The *Exersides*TM restraint (both arms) in use by an awake patient mechanically ventilated for acute lung injury and able to participate in care.

A

B

volunteers who, following consent, were videotaped and acted in both their staff role (bedside RN) and simulated patient role (performed in a hospital bed). In the patient role, volunteers were instructed to act as: 1) a calm and cooperative patient, 2) a confused patient with moving arms, and 3) an agitated patient. Results, summarized in Table 1, demonstrate high satisfaction.

3. A pilot study of first prototype *Exersides*TM restraint in ICU patients demonstrated feasibility and potential benefit. An IRB-approved pilot study was conducted in one Vermont hospital ICU, where 10 mechanically ventilated patients were alternately assigned to wear *Exersides*TM or traditional wrist restraints (n=5 in each group, 64±7 years old, 30% women). On day #3 of intubation, all patients were continuously videotaped for 4 consecutive hours while wearing their assigned device. All 5 patients in the *Exersides*TM group tolerated the device with no adverse events (defined as no self-extubation, feeding tube or IV dislodgement, self-removal of restraint, skin breakdown or bodily trauma to patient or nurse).

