

18 Patton MQ. Qualitative Research & Evaluation Methods: Integrating Theory and Practice. 4th ed. Thousand Oaks, CA: Sage Publications, 2015;

20 Nalamalapu SR, [name] DM, [name] RD. Patient Recruitment Rate in Multicentered Randomized Trials in Critical Care. *Crit Care Med* 2016; 44:e588-589

Objectives: Clearly state the primary and secondary objective(s) of the study.

Phase I Specific Aims:

1. To revise the *ExersidesTM* prototype based on feedback obtained from standardized patients in the UVM simulation center.
2. To demonstrate that the revised *ExersidesTM* restraint is safe, and that conducting the proposed RCT (for STTR Phase II) is feasible, by performing a prospective evaluation in 8 mechanically ventilated older patients who require wrist restraint, including pilot testing all proposed measurements and outcomes planned for STTR Phase II

Milestones to progress to Phase II: (A) Demonstrate that the revised *ExersidesTM* prototype is safe in older mechanically ventilated patients who require restraint (i.e., has mean incidence <20% across pre-defined safety criteria, including: skin breakdown and laceration, reportable injuries to patients and clinicians, self-removal of the restraint, and damage to ICU bed or equipment), and (B) Demonstrate feasibility of the RCT planned for STTR Phase II, including enrollment of 8 ICU patients and completion of >90% of all outcomes/measures.

Phase II Specific Aims:

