- Description of restraint intervention:** All 8 patients will wear both the *Exersides™* and traditional wrist restraint devices on both arms, sequentially, over 2 study days. On Day 1, they will wear the *Exersides™* restraint on both arms from 9am-1pm and wrist restraints on both arms from 1pm-5pm. On Day 2, they will wear the restraints on both arms in the opposite order. During each 4-hour period, subjects will be observed by research and nursing staff, with validated and reliable hourly assessments of sedation/agitation (RASS) status,¹ and validated and reliable delirium assessment (CAM-ICU) at the start and stop of each period (see Aim 3, Outcome 2 for description of RASS and CAM).¹ Subjects will wear actigraphs on both wrists to measure mobility/activity continuously. A digital video camera will be set up at the foot of the patient's bed to continuously record his/her movements during the study sessions. Overnight between Days 1 and 2, subjects will resume traditional restraints, per MD order. Intervention ends on Day 2. Satisfaction/acceptability/perceptions of device will be assessed in nurses, family members, physicians, and patients as per RCT protocol (see Aim 3, Outcome 3).
- Phase I Outcomes:**

1. Demonstrate that revised prototype is safe, with <20% mean incidence across 7 safety criteria in the 8 subjects enrolled. Safety criteria in STTR Phase I will include: 1) clinician or patient laceration (Grade 2b or higher, per STAR laceration grading criteria⁹) from any sharp edges of device, 2) development of pressure ulcer from device of Stage 3 or greater per 2016 National Pressure Ulcer Advisory Panel Pressure Injury Stages,¹⁰ 3) reportable injury (per local institutional standards) of patient by device, 4) reportable injury (per local institutional standards) to clinician by device, 5) self-removal of device, 6) damage to hospital bed rendering it non-functional, and 7) damage to ICU equipment (e.g. ventilator) rendering it non-functional..
2. Demonstrate that conducting the proposed RCT in Aim 3 is feasible, by consent/recruitment rate and pilot testing measures/outcomes for the RCT, via the following tasks:
 - **Consent/Recruitment:** 8 patients consented and enrolled within ≤ 7 months

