which time they will be observed by research and nursing personnel, with validated and reliable hourly assessments of sedation/agitation (RASS score). A digital video camera will be set up at the foot of the patient's bed to continuously record his/her movements during the study sessions. Overnight between study Days 1-2 and 2-3, subjects will resume traditional wrist restraints, as per MD order. No sensor or video data will be recorded during overnight periods when study staff are not available. Starting on Day 3 morning, subjects who continue to require restraints (per MD order) will be placed in either traditional or novel restraints device, as per their original randomization (i.e. the device worn for first 4-hr study period on Day 1) for up to 4 more days (i.e. until earliest of restraints no longer needed, death, or ICU discharge). This novel within-patient crossover design allows for increased precision with fewer subjects (see Sample Size) because it controls for confounding effects of patient-specific characteristics via each patient serving as their own control when comparing outcomes (i.e. arm activity) of the novel vs. traditional restraint during Days 1 and 2, along with reduced bias due to randomized allocation of initial study group (novel vs. traditional). Moreover, this design permits more prolonged comparison of novel vs. traditional device (over Days 3 to 6) to measure secondary outcomes (e.g., agitation, delirium, and medication use) that are more accurately evaluated over longer periods of evaluation. The randomization feature of this study design also controls for potential temporal differences in movement (e.g., patient more awake/mobile from 9am-1pm vs. 1pm-5pm). Patient eligibility criteria also help ensure that the study occurs when patients require restraint and are readily assessed for the primary and secondary outcome measures.

- Recurrence of clinical need for restraint and/or ICU readmit:** If a patient ceases to need restraint during the 6-day study period, but then is deemed to need restraint again, the randomly allocated intervention will resume (up to 6-day maximum), with study ending upon ICU discharge (without re-starting if ICU re-admit).

Table 7: Primary & Secondary Outcomes of Efficacy RCT in Aim 3

Outcome		Instrument	Scale	Assessment Timing
Primary Outcome				
1	Upper extremity mobility	Actigraphy (total activity counts per 4 hours)	Continuous	Continuously throughout study
Secondary Outcomes				

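### The two Phase I skin criteria register only severe injury after 8 hours of wear, and no rule assures that milder device-related pressure injury is recorded before the longer RCT wear

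*Combined protocol and SAP*

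**What the plan says.** **Criteria.** Phase I, Aim 2 (Phase I Outcomes, item 1) sets seven safety criteria. Two are specific to skin. Criterion 1 is "clinician or patient laceration (Grade 2b or higher, per STAR laceration grading criteria", limited to sharp edges of the device. Criterion 2 is "development of pressure ulcer from device of Stage 3 or greater". Criterion 3 has no grade: "reportable injury (per local institutional standards) of patient by device". The local standards are not given.

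**Other wording.** The milestone under Objectives names "skin breakdown and laceration, reportable injuries to patients and clinicians" with no severity cut-off. The pilot's adverse-event definition (Preliminary Studies and Data, item 3) includes "self-removal of restraint, skin breakdown or bodily trauma to patient or nurse", also ungraded. Potential Risks lists skin breakdown among the device's risks.

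**Exposure.** On Phase I Day 1 patients wear the novel "restraint on both arms from 9am-1pm and wrist restraints on both arms from 1pm-5pm". The order is reversed the next day. Traditional restraints are used overnight, and the intervention ends on Day 2. In the RCT (Implementation of the RCT intervention, Study design) Days 1 and 2 give the same two 4-hour sessions. From Day 3, patients still under a restraint order stay in the device they wore first, "for up to 4 more days (i.e. until earliest of restraints no longer needed, death, or ICU discharge".

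**Recording and review outside the milestone.** Events of Interest are collected daily, through day 3 in the pilot. The section names skin laceration, upper-extremity joint pain and equipment damage. Other adverse events are collected only if both unexpected and related to the device. The engineer reports on Phase I before the device is used in the RCT, and the DSMB reviews Phase I data at its pre-RCT meeting.

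**Milestone.** Mean incidence across the criteria must be below 20% under Objectives and Aim 2, but below 5% in the opening summary.

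**The concern.** Phase I is the only planned look at the revised device in patients before the RCT. Its two skin criteria start at the severe end of the scale, after a short exposure, while the pilot definition and the milestone wording use an ungraded term. The plan gives no reason for the cut-offs.

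The early sign of a skin problem would be the milder injuries. Criteria 1 and 2 cannot register them. Whether they appear anywhere else depends on an undefined local standard or on an events list that does not name pressure injury. If they are not recorded, neither the engineer deciding on device changes nor the DSMB can take them into account before novel-first patients move to longer wear.

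**Working it through.** The plan derives no figure for this point: the milestone is a chosen threshold, and N=8 rests on feasible enrollment. The check is direct arithmetic.

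**1. Wear per patient, novel device.**
- Phase I (Aim 2): 4 h + 4 h = 8 h.
- RCT, Days 1-2: 8 h.
- RCT, Days 3-6, novel-first patients only: up to 4 days. Hours per day are not stated, so a range is shown.

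| Assumed wear on Days 3-6 | RCT total | Ratio to 8 h |
|---|---|---|
| 8 h/day | 8 + 32 = 40 h | 5 |
| 12 h/day | 8 + 48 = 56 h | 7 |
| Day 3 9am to Day 6 5pm, continuous | 8 + 80 = 88 h | 11 |
| 24 h/day for 4 days | 8 + 96 = 104 h | 13 |
| Allocated to traditional restraint | 8 + 0 = 8 h | 1 |

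The middle three totals, like the first, assume that restraint is still ordered throughout; wear ends earlier if it is not.

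**2. What the milestone can register.** Assume each of 8 subjects counts at most once per criterion. Mean incidence is then events / (8 x 7) = events / 56.
- Below 20% allows up to 11 events: 11/56 = 19.6%.
- Below 5% allows up to 2 events: 2/56 = 3.6%, while 3/56 = 5.4% fails.

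**3. Sub-threshold skin injury in all 8 patients.**
- Criteria 1 and 2: 0 of 16 cells, by definition.
- Criterion 3: 0 to 8 cells, depending on local reportability.
- Mean: 0/56 = 0% to 8/56 = 14.3%.

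The upper end passes the <20% milestone and fails the <5% one. Under <5%, three locally reportable minor injuries are enough to fail.

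**4. Effect of lowering the cut-off alone.** If milder injury counted under one skin criterion and occurred in all 8 patients, with no other event, the mean would again be 8/56 = 14.3%. That still passes <20%.

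**5. Precision.** Even 0/8 on a criterion leaves a one-sided 95% upper bound of 1 - 0.05^(1/8) = 31.2%. A clean count of severe events in 8 patients says little by itself, which adds to the value of the milder grades.

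**6. Capture outside the milestone.** Laceration is named as an event of interest without a grade, so milder lacerations have a route to the database. Pressure injury is not named. The list is introduced as examples, so recording is possible but not assured. The adverse-event route adds the condition that the event be judged unexpected.

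**The case against.** The strongest reply is that the milestone is not the only safeguard. Criterion 3 is ungraded. The events-of-interest list is open-ended and explicitly takes in events that are not serious. Unexpected adverse events related to the device to any degree must be reported within 24 hours. The principal investigator monitors Phase I, and both the engineer and the DSMB see Phase I results before the RCT. A severity cut-off is also defensible, because the same arms wear wrist restraints for 4 hours each day and overnight, which makes minor lesions hard to attribute.

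Much of this stands, and it rules out several stronger readings:

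- A reader might infer that milder skin injury in every patient must score 0%. That is certain only for criteria 1 and 2; criterion 3 could raise the mean to 14.3%.
- A reader might infer that the skin criteria are almost bound to read zero. The documents give no incidence or time course of pressure injury by hours of wear, and a sharp-edge laceration need not depend on long wear.
- A reader might take the RCT exposure as 13 times that of Phase I. That is the upper limit under continuous wear, in novel-first patients only.
- A reader might infer that the milestone wording contradicts the criteria, or that the pilot counted every grade. The milestone text summarises criteria defined later, and the pilot definition is silent on grade.
- A reader might infer that lowering the cut-off would change the go/no-go decision. Under <20% it would not by itself do so; averaging over seven criteria dilutes it.

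What the reply does not supply is a rule that a Stage 1 or 2 device-related pressure injury is recorded. Reviewers can act only on what was collected.

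**Conclusion.** The concern holds as a gap in capture, not as proof that the milestone is blind to skin harm. Criteria 1 and 2 cannot register milder injury. Criterion 3 may, on an undefined standard. Outside the milestone, pressure injury is not a named event. The size is 0% to 14.3% on the milestone for milder injury in all 8 patients, ahead of a 5- to 13-fold longer wear in novel-first patients. These figures assume one count per subject per criterion, a restraint order lasting through Day 6, and 8 to 24 hours of wear per day.

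Whether to redefine the go/no-go events is a debatable trade-off and is not needed to close the gap. Recording and reporting all grades is a cheap improvement that changes what Phase I can detect. Separately, the two milestone thresholds give different answers on the same data and must be reconciled; the documents do not settle which was intended.

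**What to change.** 1. **Events of Interest:** add device-related pressure injury of any stage and laceration of any grade to the daily list, with the stage or grade recorded.
2. **Aim 2, Phase I Outcomes:** keep the Stage 3+ and Grade 2b+ counts as the severity line, and report the all-grade counts beside the milestone.
3. **Phase I Study follow-up and Data Safety Monitoring Plan:** provide the all-grade counts to the engineer for the device report and to the DSMB at its pre-RCT review.
4. **Criterion 3:** state which skin events count as reportable, and whether one lesion may count under more than one criterion.
5. **Milestone:** reconcile the opening summary, Objectives and Aim 2 on the threshold and on the description of the skin events.

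The cost is a few lines of protocol text and a stage/grade field on the case report form. The downside is that reported minor skin events will rise, and some will be hard to attribute because the same arms also wear wrist restraints. Recording the site of each lesion and the device in place would limit that problem but not remove it.

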The goal of this Fast-Track STTR project is to optimize and test a novel arm restraint in older critically ill mechanically ventilated patients that increases mobility; reduces agitation, use of sedative medications, and delirium; and exhibits high satisfaction and acceptability among hospital staff, family members, and patients. Older mechanically ventilated patients are often immobilized with wrist restraints to prevent self-extubation and are sedated to reduce agitation caused by their restraints and endotracheal (breathing) tube. This sedation and immobility lead to complications, including delirium and muscle weakness, that are independently associated with long term cognitive impairment, reduced physical functioning, and mortality. Specifically, the incidence and duration of delirium in the ICU are strongly and independently associated with long-term cognitive impairment that is similar to Alzheimer's Disease and Related Dementias.

Healthy Design is developing the novel *Exersides*TM restraint that allows arm mobility but prohibits hands from reaching oral/nasal endotracheal and feeding tubes or intravenous lines. Because it permits mobility, *Exersides*TM may reduce agitation and the need for sedatives. In preliminary pilot testing, *Exersides*TM has demonstrated very encouraging results. The objectives of this STTR Fast-Track project are to optimize *Exersides*TM and evaluate it in a randomized controlled trial (RCT) in older critically ill patients at high risk for delirium and associated long-term cognitive impairment. The multidisciplinary investigator team has expertise in critical care, extensive experience in conducting ICU RCTs, and a history of successful collaboration.

During Phase I, a prospective study will be performed in 8 older mechanically ventilated patients to demonstrate that 1) the revised *Exersides*TM prototype is safe and 2) the RCT proposed in Phase II is feasible. The milestones to proceed to Phase II are to demonstrate that: 1) the revised *Exersides*TM restraint has mean incidence rate <5% across 7 pre-specified safety criteria in mechanically ventilated

older patients who require restraint; and 2) the RCT in phase II is feasible by successfully enrolling 8 ICU patients into the phase I study and completing at least 90% of all proposed outcome measures.

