 - **Outcomes/measures:** At least 90% of all outcomes planned for the RCT in Aim 3 (STTR Phase II) will be measured in the 8 patients: 1) actigraphy counts, 2) RASS sedation/agitation score,¹ 3) CAM-ICU delirium score,¹ 4) medication use, 5) satisfaction/acceptability/perceptions of novel restraint. Incidence of self-extubation will also be reported in addition to the following measures of efficacy: 1) patient-reported satisfaction measures including comfortable, safe, effective, preferable and more humane; and 2) staff-reported satisfaction measures including easy to don/doff, easy to change level, safe for staff, effective, preferable and more humane. See Aim 3 for these RCT measures.

- **Data collection/management, quality assurance & analysis:** See Aim 3.
- **Sample size:** N=8 was based on feasible enrollment from the single study site during the 9-month Phase I period (i.e., ~1 patient/month). Literature suggests that there is no advantage to including more than 6-10 subjects per group in a Phase I study, and most chemotherapeutic phase I studies have N=3 per cohort.¹ Thus, N=8 is adequate for the proposed Aims to prepare for the RCT in Aim 3.
- **Phase I Study follow-up.** The engineer will prepare a report on the outcomes of all assessments based upon STTR Phase I, and will decide (in consultation with the project leadership team) which device improvements/modifications will be required before use of device in Aim 3 (STTR Phase II).

PHASE II (3-site RCT to compare the novel restraint to traditional wrist restraints)

[figure not shown]
Aim 3: To conduct a multi-site, within-patient randomized crossover trial in older critically ill mechanically ventilated patients who require restraint, to compare the *Exersides™* restraint vs. traditional wrist restraints.

Overview and Study Design Phase II. The objective of the Phase II project is to conduct an RCT to measure 3 outcomes:

1. Mobility/activity evaluated by actigraphy (primary outcome)
2. Agitation, delirium, medication use (sedative, analgesic, and antipsychotic), and incidence of self-extubation (secondary outcomes)
3. Satisfaction with, and acceptability/perceptions of, the device by patient, family, and clinicians (secondary outcomes)

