Potential risks from the *Exersides*TM restraint device are very low. Our own preliminary data demonstrate safety in that no adverse or severe adverse events (i.e. no self-removal of endotracheal tubes, feeding tubes, intravenous lines, etc.) – these preliminary data are from a pilot study that has already taken place that enrolled critically ill patients in a single intensive care unit. Although self-removal of tubes and lines is a risk, as occurs with any existing currently available restraint device, we anticipate that this risk is very low due to the design of the *Exersides*TM restraint that intentionally was created to further reduce this risk in comparison to traditional restraints. Other potential risks include skin breakdown from the *Exersides*TM restraint device, and a theoretical increased risk of increased removal of upper extremity peripheral IVs, but we did not observe any of these events in our pilot study.

There are few alternative treatments to participating in this RCT. Use of the *Exersides*TM restraint device is not standard of ICU care at any clinical center. However, this study will not alter clinical care that occurs with regard to other aspects of critical illness. Specifically, only patients whose physicians have already written an order requiring physical restraints will be considered for the study. The novel *Exersides*TM restraint device will only be used while such an order is active, as part of routine clinical care (i.e. no patient will receive the *Exersides*TM restraint device without a need for physical restraint as documented/ordered by the ICU clinicians). All study sites currently follow (and will continue to follow throughout the duration of the study) Joint Commission requirements for re-assessment and re-ordering restraints at least once every 24 hours. If a restraint is no longer required/ordered as part of routine clinical care, then use of the *Exersides*TM restraint device will immediately stop and not re-start unless a renewal of a restraint order is done, as required by clinical circumstances. In no way will the study have any influence over the ordering of restraints as part of clinical care in the ICU.

ADEQUACY OF PROTECTION AGAINST RISKS

Recruitment and Informed Consent

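### The seven Phase I safety criteria do not name self-extubation or removal of tubes and lines, so the go/no-go rule sets no limit on either

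*Combined protocol and SAP*

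**What the plan says.** Phase I Outcomes, item 1 (Aim 2) sets the rule: "Demonstrate that revised prototype is safe, with <20% mean incidence across 7 safety criteria in the 8 subjects enrolled". Its first four criteria are laceration, pressure ulcer of Stage 3 or worse, patient injury and clinician injury. The patient-injury item reads "reportable injury (per local institutional standards) of patient by device". Criteria 5 to 7 are "5) self-removal of device, 6) damage to hospital bed rendering it non-functional, and 7) damage to ICU equipment (e.g. ventilator) rendering it non-functional".

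The milestone under Phase I Specific Aims repeats these kinds of event, again with the test that the prototype "has mean incidence <20% across pre-defined safety criteria". Its wording makes clear that self-removal refers to the restraint, not to a tube. The opening project summary states a different limit: the device "has mean incidence rate <5% across 7 pre-specified safety criteria".

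Self-extubation appears in item 2 of the Phase I Outcomes, under feasibility: "Incidence of self-extubation will also be reported in addition to the following measures of efficacy". No limit is attached. Removal of a feeding tube or line is not a named Phase I outcome.

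Elsewhere the protocol treats these events as safety matters. The pilot study (Preliminary Studies, item 3) reported no adverse events, "defined as no self-extubation, feeding tube or IV dislodgement, self-removal of restraint, skin breakdown or bodily trauma to patient or nurse". Background and Significance gives prevention of self-extubation as a design purpose of the device. Potential Risks says "Although self-removal of tubes and lines is a risk", and adds that this is so for any restraint now available.

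**The concern.** The device lets the arm move while keeping the hand away from tubes and lines. The failure of most interest in a first study of the revised prototype is therefore a patient reaching a tube. The Phase I list keeps the pilot's other adverse events (restraint removal, skin damage, bodily injury) and leaves out self-extubation and tube or line dislodgement.

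The milestone is the only numerical test of safety between Phase I and a 54-patient RCT. As written, a restraint that stays on, injures no one and breaks nothing meets it, however often patients reach their tubes. The omission may also narrow Aim 1, which directs device refinement at the safety issues listed in Aim 2.

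**Working it through.** The plan's figure is a threshold, not a derived quantity, and N=8 is justified by feasible enrolment, so there is no power or error rate to reproduce. The check is to apply the rule.

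**Inputs.** 8 patients and 7 criteria (Phase I Outcomes, item 1). Limits of <20% (Aim 2 and the milestone) and <5% (opening summary).

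**Assumptions.** Incidence is counted per patient and the criteria carry equal weight; the protocol does not say otherwise. Then mean incidence = (sum over criteria of patients with the event) / (8 × number of criteria), and the denominator is 8 × 7 = 56.

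**What the rule tolerates.** At <20%: 11/56 = 19.6% passes and 12/56 = 21.4% fails. At <5%: 2/56 = 3.6% passes and 3/56 = 5.4% fails.

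**Self-extubation under the seven criteria**

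| Scenario | Score | <20% | <5% |
|---|---|---|---|
| Every intubated patient, no listed event | 0/56 = 0% | pass | pass |
| 3 events logged under criterion 3 (or 5) only | 3/56 = 5.4% | pass | fail |
| 8 events logged under criterion 3 only | 8/56 = 14.3% | pass | fail |
| 8 events logged under both criteria 3 and 5 | 16/56 = 28.6% | fail | fail |

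The first row holds however many of the 8 are intubated. The other rows depend on whether a site treats a self-extubation as a reportable injury by the device, or whether the patient got free by removing the restraint. The local reporting standards are not in the protocol.

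**Adding the events to the mean**

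- Self-extubation as an eighth averaged item, 8 of 8: 8/64 = 12.5%. Passes <20%, fails <5%.
- Self-extubation and tube or line removal as items eight and nine, 8 of 8 on the first only: 8/72 = 11.1%. Passes <20%, fails <5%.
- Both at 8 of 8: 16/72 = 22.2%. Fails both.

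At the 20% limit, averaging hides self-extubation in every patient even when it is listed. A separate limit is needed.

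**What a separate limit could do with 8 patients.** The documents give no usable event rate, so the per-patient risk p is an assumption. P(at least one event) = 1 − (1 − p)^8.

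| Assumed p | P(at least one of 8) |
|---|---|
| 5% | 34% |
| 10% | 57% |
| 20% | 83% |
| 30% | 94% |

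These are also the chances that a zero-event limit would stop the device. They describe the cost of a strict limit; they do not measure the omission. With 0 of 8 events the one-sided 95% upper bound is 1 − 0.05^(1/8) = 31.2%.

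**The case against.** The best defence is that the seven criteria mainly cover harm or damage done by the device, while self-extubation is a matter of how well it works. The protocol reports it beside efficacy measures in Phase I and makes it a secondary outcome in the RCT, where there is a randomised comparator. Each Phase I patient wears the new restraint for two 4-hour periods under observation, and the 31.2% bound shows how little 8 patients can establish. This argues for modesty about any limit. It does not explain why the pilot's own adverse events were dropped from the safety list.

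There are also backstops. The engineer reports on all assessments and decides with project leadership on modifications before Aim 3. The principal investigator monitors safety in Phase I. The DSMB, convened at the end of Phase I, reviews Phase I data before the RCT and can recommend changes or stopping. A reader might infer that a failing device would go to 54 patients unnoticed; the documents do not support that. What stands is that none of these reviews has a stated limit, and removal of tubes and lines may not have been collected systematically for them to see.

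Three other stronger readings fail:

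- **That no self-extubation could ever fail the gate.** An event counted under criterion 3 or 5 enters the mean, and three such events exceed 5%.
- **That all 8 patients could self-extubate.** Table 4 admits patients on non-invasive ventilation, so the statement applies to those intubated.
- **That the protocol regards tube removal as a risk peculiar to this device.** Potential Risks presents it as common to all restraints and expects it to be lower here. The theoretical increase it mentions concerns peripheral IVs.

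The milestone introduces its examples with an open word, so the list might be thought extensible. Aim 2 and the opening summary both fix the number at seven, and Aim 2 enumerates them.

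**Conclusion.** The concern holds as an omission from the decision rule. Followed as written, the rule gives 0/56 when every intubated patient self-extubates without any listed event. On the generous reading, with all 8 counted as reportable injury, it gives 14.3%, still within the 20% limit stated in two places. It fails only against the 5% limit stated once. The conflict between the two limits is a separate matter and needs reconciling, but it decides how much protection criterion 3 could give.

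The conclusion assumes per-patient counting and equal weights. The 0% also assumes that the event is not logged under criterion 3 and does not come about through removal of the restraint. The gap is best described as the lack of any prespecified limit for the event the device is meant to prevent, together with the lack of a named Phase I measure of tube and line removal.

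**What to change.** 1. Add two criteria to Phase I Outcomes, item 1, and to the milestone under Phase I Specific Aims: self-extubation, with intubated patients as the denominator, and self-removal of a feeding tube or vascular line.
2. Record which restraint was worn at the time, since every patient alternates between the two and returns to wrist restraints overnight.
3. Judge each new criterion on its own, outside the mean.
4. Have the study leadership and the principal investigator responsible for Phase I monitoring fix the limit for each, in writing, before Phase I data are reviewed. The choice is theirs; this review proposes no value.
5. State whether an event that also meets criterion 3 or 5 is counted there too.

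**Cost.** Self-extubation is already reported, and the study sessions are already observed and filmed. Tube and line removal needs one added data item. The gate becomes harder to pass by an amount that depends on the limit. At the strictest, a zero-event limit on one criterion would stop the device with probability 57% or 83% if the true per-patient risk were 10% or 20% (assumed values, all 8 patients at risk). That trade-off should be set out when the limit is chosen.
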